## 5.7 Treatment Compliance

Subjects will be encouraged to comply with all study-related medications by the Investigator, pharmacist, and research coordinator. Subjects will be given a pill diary to track medication that has been taken. Subjects will bring all bottles of unopened or unused study drug with them to each visit. Unused drug tablets will be counted for compliance and recorded. Treatment compliance of nivolumab will be documented in the electronic medical record.

## 6.0 TREATMENT DURATION

Patients will complete therapy unless one of the following criteria applies:

- Confirmed Disease progression per iRECIST
- Intercurrent illness that prevents further administration of treatment
- Unacceptable adverse events
- Patient withdrawal from study (patient choice)
- Pregnancy
- Failure of patient to adhere to study requirements
- Physician Discretion
- Study termination
- Patient receives alternative treatment

### 6.1 Discontinuation Criteria

#### 6.1.1 Discontinuation Due to Disease Progression

Immunotherapeutic agents such as BMS-986205 and nivolumab may produce antitumor effects by potentiating endogenous cancer-specific immune responses. The response patterns seen with such an approach may extend beyond the typical time course of responses seen with cytotoxic agents and can manifest as a clinical response after an initial increase in tumor burden or even the appearance of new lesions.

Immune RECIST will be used for assessment of tumor response for the purposes of managing subjects on study treatment and decision-making for discontinuation of study therapy due to disease progression. PD should be confirmed no earlier than 4 weeks later according to the criteria outlined in Table 2. Subjects who are deemed clinically unstable or who have biopsy proven new metastatic lesions are not required to have repeat imaging for confirmation. This decision will be based on the Investigator's clinical judgment of a subject's overall clinical condition, including performance status, clinical symptoms, and laboratory data. At a minimum, subjects must meet the below criteria for continued treatment on study after disease progression is identified at a tumor assessment.

When feasible, subjects should not be discontinued until progression is confirmed; however, the decision to continue study treatment after the first evidence of disease progression is at the Investigator's discretion based on the clinical status of the subject.

Subjects may receive study treatment while waiting for confirmation of PD if they are clinically stable as defined by the following criteria:

- No decline in ECOG performance status.
- Absence of new or worsening symptoms.
- Absence of rapid progression of disease.
- Absence of progressive tumor at critical anatomical sites (e.g., spinal cord compression) requiring urgent alternative medical intervention.

### **6.1.2 Discontinuation from Study Treatment**

Participants MUST discontinue investigational product (and non-investigational product at the discretion of the investigator) for any of the following reasons:

- Participant's request to stop study treatment. Participants who request to discontinue study treatment will remain in the study and must continue to be followed for protocol specified follow-up procedures. The only exception to this is when a participant specifically withdraws consent for any further contact with him/her or persons previously authorized by participant to provide this information
- Any clinical adverse event (AE), laboratory abnormality or intercurrent illness which, in the opinion of the investigator, indicates that continued participation in the study is not in the best interest of the participant
- Termination of the study by Bristol-Myers Squibb (BMS)
- Loss of ability to freely provide consent through imprisonment or involuntarily incarceration for treatment of either a psychiatric or physical (e.g., infectious disease) illness. (Note: Under specific circumstances, a participant who has been imprisoned may be permitted to continue as a participant. Strict conditions apply and BMS approval is required).
- Additional protocol-specified reasons for discontinuation.

In the case of pregnancy, the investigator must immediately notify the PI of this event. In the event a normal healthy female participant becomes pregnant during a clinical trial, the study treatment must be discontinued immediately. In most cases, the study treatment will be permanently discontinued in an appropriate manner (e.g., dose tapering if necessary for participant safety). Please notify the PI within 24 hours of awareness of the pregnancy. If the investigator determines a possible favorable benefit/risk ratio that warrants continuation of study treatment, a discussion between the investigator and the PI must occur.

The assessment for discontinuation of nivolumab should be made separately from the assessment made for discontinuation of BMS-986205. Although there is overlap among the discontinuation

criteria, if discontinuation criteria are met for BMS-986205 but not for nivolumab, treatment with nivolumab may continue if BMS-986205 is discontinued.

If a participant in any of the nivolumab/BMS-986205 combination arms meets criteria for discontinuation and investigator is unable to determine whether the event is related to both or one study drug, the participant should discontinue both nivolumab and BMS-986205 and be taken off the treatment phase of the study.

#### **6.1.3 Discontinuation of BMS-986205**

BMS-986205 treatment should be permanently discontinued for the following:

- Any event requiring discontinuation of nivolumab as in Section 6.1.2
- Any event requiring more than 1 dose reduction of BMS-986205 (see Section 5.5.2)
- Any AE, laboratory abnormality, or intercurrent illness which, in the judgment of the investigator, presents a substantial clinical risk to the participant with continued BMS-986205 dosing
- For participants who delay BMS-986205 but continue nivolumab, any dose delay of BMS-986205 lasting > 10 weeks due to toxicity attributable to BMS-986205 and not nivolumab (e.g., methemoglobin, hemolysis, or QTc >500 msec) will result in the discontinuation of BMS-986205 only, and participants may continue treatment with nivolumab after discussion with the PI.
- Any occurrence of serotonin syndrome

#### **6.1.4 BMS-986205 and Nivolumab Discontinuation Due to AEs**

BMS-986205 and nivolumab treatment should be permanently discontinued for the following:

- Any Grade 2 drug-related uveitis, eye pain or blurred vision that does not respond to topical therapy and does not improve to Grade 1 severity within 2 weeks of starting therapy OR requires systemic treatment
- Any event requiring more than 1 dose reduction of BMS-986205
- Any Grade 3 non-skin, drug-related AE lasting > 7 days or recurs, with the following exceptions:
  - Grade 3 drug-related uveitis, pneumonitis, bronchospasm, neurologic toxicity, myocarditis, hypersensitivity reaction, or infusion reaction of any duration requires discontinuation.
  - Grade 3 drug-related endocrinopathies, adequately controlled with only physiologic hormone replacement do not require discontinuation. Adrenal insufficiency requires discontinuation regardless of control with hormone replacement.

- Grade 3 drug-related laboratory abnormalities do not require treatment discontinuation except:
  - Hepatic events should be managed as detailed in Section 5.6.4
  - Grade 3 drug-related thrombocytopenia > 7 days or associated with bleeding requires discontinuation
  - Grade  $\geq 3$  drug-related AST, ALT or total bilirubin requires discontinuation\*
  - Concurrent AST or ALT  $> 3 \times$  ULN and total bilirubin  $> 2 \times$  ULN

\* In most cases of Grade 3 AST or ALT elevation, study treatment will be permanently discontinued. If the investigator determines a possible favorable benefit/risk ratio that warrants continuation of study treatment, a discussion between the investigator and BMS must occur.

- Any Grade 4 drug-related AE or laboratory abnormality (including but not limited to creatinine, AST, ALT, or Total Bilirubin) except for the following events which do not require discontinuation:
  - Grade 4 neutropenia  $\leq 7$  days.
  - Grade 4 lymphopenia or leukopenia or asymptomatic amylase or lipase.
  - Isolated Grade 4 electrolyte imbalances/abnormalities that are not associated with clinical sequelae and are corrected with supplementation/appropriate management within 3 calendar days of their onset.
  - Grade 4 drug-related endocrinopathy AEs, such as, hyper- or hypothyroidism, or glucose intolerance, which resolve or are adequately controlled with physiologic hormone replacement (corticosteroids, thyroid hormones) or glucose-controlling agents, respectively, may not require discontinuation after discussion with and approval from the PI.
- Any AE, laboratory abnormality, or intercurrent illness which, in the judgment of the investigator, presents a substantial clinical risk to the participant with continued BMS-986205 and nivolumab dosing.
- Any event that leads to delay in dosing lasting  $> 10$  weeks from the previous dose requires discontinuation, with the following exceptions:
  - Dosing delays to allow for prolonged steroid tapers to manage drug-related AEs are allowed.
  - Dosing delays lasting  $> 10$  weeks from the previous dose that occur for non-drug-related reasons may be allowed if approved by the PI.

Prior to re-initiating treatment in a participant with a dosing delay lasting  $> 10$  weeks, the PI must be consulted. Tumor assessments should continue as per protocol even if dosing is delayed.

Periodic study visits to assess safety and laboratory studies should also continue every 4 weeks or more frequently if clinically indicated during such dosing delays.

Participants who are discontinued from nivolumab, must also discontinue BMS-986205.

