### **5.5.2.2 BMS-986205 Dose Modifications**

A dose reduction of BMS-986205 is defined as a change from a 100 mg QD tablet to a 50 mg QD tablet.

Doses of BMS-986205 should be reduced for the following AEs attributable to study therapy that do not otherwise meet criteria for discontinuation:

- Grade 3 fatigue, nausea, vomiting, or anemia related to study treatment
- Methemoglobin  $\geq 15\%$
- Clinically significant elevations in methemoglobin (generally 10%, with a normal hemoglobin level) with any associated Grade 3 AE (hypoxia, dyspnea, confusion, etc.) attributable to sustained elevations of methemoglobin and not attributable to another etiology
- QTcF  $> 500$  msec confirmed by at least 1 repeat ECG and at least 60 msec above baseline

Dose modification and interruption of BMS-986205 may occur in the setting of lower grade AEs and/or be more conservative than indicated above based on the clinical judgment of the PI. For an AE requiring dose modification, BMS-986205 should be interrupted to allow improvement of the AE, even if the AE does not otherwise meet criteria for dose delay.

Re-escalation of BMS-986205 will not be permitted once the dose of BMS-986205 has been reduced for a participant.

Only one dose reduction is permitted. The participant must discontinue study treatments if a subsequent dose reduction of BMS-986205 is required.

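### The stopping rules do not consistently say whether a BMS-986205 toxicity stops that drug alone or nivolumab as well

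*Combined protocol and SAP*

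**What the plan says.** Section 6.1.2 sets a general principle: "The assessment for discontinuation of nivolumab should be made separately from the assessment made for discontinuation of BMS-986205". It adds that "if discontinuation criteria are met for BMS-986205 but not for nivolumab, treatment with nivolumab may continue if BMS-986205 is discontinued". The section ends with a default: if the investigator cannot tell which drug caused a qualifying event, both stop.

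Section 6.1.3 opens with "BMS-986205 treatment should be permanently discontinued for the following". Its list includes events that stop nivolumab (with a pointer to Section 6.1.2), more than one BMS-986205 dose reduction (with a pointer to Section 5.5.2), and any occurrence of serotonin syndrome. It also covers participants who stay on nivolumab while BMS-986205 is held. For them, a hold over 10 weeks for toxicity attributed to BMS-986205 and not nivolumab, with methemoglobin, hemolysis and QTc given as examples, "will result in the discontinuation of BMS-986205 only, and participants may continue treatment with nivolumab after discussion with the PI".

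Section 6.1.4 opens with "BMS-986205 and nivolumab treatment should be permanently discontinued for the following". Its list repeats "Any event requiring more than 1 dose reduction of BMS-986205". It then adds Grade 3 non-skin drug-related events that last more than 7 days or recur, Grade 4 drug-related events with listed exceptions, and dosing delays over 10 weeks with two exceptions.

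Section 5.5.2.2 says: "The participant must discontinue study treatments if a subsequent dose reduction of BMS-986205 is required".

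Section 5.5.1 holds BMS-986205 alone for specified methemoglobin and QTcF findings. It lets nivolumab go on during such holds, unless a contribution of nivolumab to an associated Grade 3 event cannot be ruled out.

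**The concern.** A site that must decide whether a patient keeps nivolumab will find the answer in more than one place, and the places differ in scope. The decision is permanent. Nivolumab is also the component for which the protocol cites response data in HCC: Section 1.4 gives 15% in dose escalation, 20% in dose expansion and 23% in patients without prior therapy.

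If two investigators read different sections, patients with the same event can have different nivolumab exposure in a small single-arm study. That affects how the patient is treated and how later response, PFS and tolerability by drug are interpreted.

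**Working it through.** The plan gives no figure to reproduce on this point, so the check is a comparison of the sections, trigger by trigger.

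**Trigger 1: more than one BMS-986205 dose reduction**

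| Section | Scope stated |
|---|---|
| 5.5.2.2 | Study treatments, in the plural |
| 6.1.2 | Drugs assessed separately; nivolumab may continue only if its own criteria are not met |
| 6.1.3 | BMS-986205; silent on nivolumab; points to 5.5.2 |
| 6.1.4 | Both drugs |

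No section says that nivolumab continues after this trigger. Stopping both drugs satisfies all four rows. This is a remark on consistency, not on which rule is right. The doubt arises because the 6.1.3 bullet is redundant if the trigger always stops both drugs, and because 6.1.3 read with 6.1.2 alone invites the other reading.

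**Trigger 2: toxicity attributed to BMS-986205 and not to nivolumab**

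- *Delay over 10 weeks.* Section 6.1.3 stops BMS-986205 only and lets nivolumab continue after discussion. Section 6.1.4, under its both-drugs lead-in, exempts only prolonged steroid tapers and approved delays that are not drug-related. A delay caused by BMS-986205 fits neither exemption. As written, the two outcomes differ.
- *Grade 3 non-skin event lasting over 7 days or recurring.* Section 5.5.1 lets nivolumab continue when a methemoglobin elevation with an associated Grade 3 event leads to a BMS-986205 hold, if nivolumab's contribution is ruled out. Section 6.1.4 stops both drugs if the event lasts or recurs, and makes no exception by attribution. It does exempt Grade 3 laboratory abnormalities, apart from listed hepatic and platelet findings, so the conflict is confined to events handled as clinical adverse events.
- *Grade 4.* Sections 5.5.1 and 5.5.2.2 call for a hold and a reduction of BMS-986205 at methemoglobin of 15% or more. Section 5.6 attaches the label Grade 4 to that level. If that grading applies in Section 6.1.4, both drugs stop, because methemoglobin is not among its Grade 4 exceptions. The reduction rule, which yields to any discontinuation criterion, would then never operate at that level.

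The default in 6.1.2 covers unclear attribution only. It does not settle events whose cause is judged to be BMS-986205. Stopping one drug is plainly intended in some cases: Section 5.5.4 does so for serotonin syndrome.

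**Pointer.** Section 6.1.3 sends the reader to 6.1.2 for events that stop nivolumab. Section 6.1.2 holds general reasons; the list of specific adverse events is in 6.1.4.

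**Rough frequency.** The protocol gives no rate for these triggers. As an upper guide, assume that the toxicity-discontinuation rates cited from the earlier combination study in advanced cancers carry over: 1.4% (Section 1.5) and 3.6% at 100 mg (Section 1.3.1).

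- 17 patients at the MTD: 17 × 0.014 = 0.24; 17 × 0.036 = 0.61.
- All 23 patients in Section 14.2: 23 × 0.014 = 0.32; 23 × 0.036 = 0.83.

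These are expected counts for any toxicity stop. Stops due to BMS-986205 alone are a subset. Section 1.3.1 reports no discontinuation for methemoglobinemia, and hemolytic anemia in 0.3% of subjects on the combination (17 × 0.003 = 0.05).

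**The case against.** The strongest reply is that the sections can be read together. Section 6.1.3 is not a list of single-drug stops, since its first item covers events that stop nivolumab. Where it means one drug, it says so, and only for the long delay. Its dose-reduction item points to Section 5.5.2, which uses the plural. That reply stands for the dose-reduction trigger. A reader might infer that 6.1.3 and 6.1.4 give opposite orders for it; they do not, because 6.1.3 never says that nivolumab goes on.

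The reply is weaker for the long delay. One can argue that the more specific 6.1.3 item prevails, or that a dosing delay in 6.1.4 means a delay of both drugs. Neither is written down. The precedence stated in Section 5.5.2.2 ranks discontinuation above dose reduction; it does not rank 6.1.3 against 6.1.4.

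Two further inferences are tempting and should not be drawn:

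- *That one section stops everything after 7 days while the other allows 70 days (10 × 7) on nivolumab for the same event.* The 7 days measure how long an event stays at Grade 3; the 10 weeks measure how long dosing is held. A hold can outlast Grade 3, because Section 5.5.6 generally requires recovery to Grade 1 or baseline, and most Grade 3 laboratory findings are exempt.
- *That the ambiguity could overturn the rule of at least 3 responses in 17.* One patient is 1/17 = 5.9 percentage points, but that is true of any patient. The affected patient would also have to be a non-responder at the stop who would have responded later on nivolumab alone. The documents give no rate for that.

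It is also fair that the planned safety summary in Section 14.4 does not list discontinuations by drug, so no planned table is shown to change.

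**Conclusion.** The point holds as an inconsistency in the stopping rules, of moderate importance. The scope of the second-reduction trigger for nivolumab is ambiguous. For toxicity attributed to BMS-986205 alone, the sections conflict on delays over 10 weeks, and they can conflict on prolonged Grade 3 clinical events and non-exempt Grade 4 events. The pointer in 6.1.3 is incomplete.

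The consequence is inconsistent nivolumab exposure and handling, probably in fewer than one patient on average. That size assumes that the cited discontinuation rates apply to patients with HCC; if hepatic disease raises toxicity, it would be larger. The design's alpha and power do not depend on these rules. Under Section 11.5.4, eligible patients who stop early stay in the response-rate analysis, so the denominator is safe.

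**What to change.** Reconcile Sections 5.5.1, 5.5.2.2, 6.1.2, 6.1.3 and 6.1.4, preferably in one table. For each trigger, state whether BMS-986205 alone or both drugs stop: a second BMS-986205 reduction; methemoglobin, hemolysis and QTc events attributed to BMS-986205; Grade 3 events that persist or recur; Grade 4 events; and delays over 10 weeks. Say which section governs if two apply. Correct the pointer from 6.1.3 to 6.1.2 and, in the same pass, the reference in 6.1.4 to a Section 5.6.4 that does not exist. Which rule applies to each trigger is for the sponsor to decide.

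On the case report form, record a stop date and a reason for each drug. Section 8.0 asks only for the reason for withdrawal from the study.

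The cost is wording in the next amendment and a small form change. No patients, visits or procedures are added.

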### **5.5.3 Protocol-Specific Recommendation for Management of Hepatic Events**

Subjects with advanced HCC generally have underlying cirrhosis with decreased hepatic function. They may also have a concomitant chronic viral infection. For this study, the upper limits for inclusion were therefore adjusted to account for baseline liver dysfunction. Subjects with AST or ALT elevations within the CTCAE Grade 2 range are allowed to enroll in the study. This requires a protocol-specific approach for the management of hepatic events outlined as follows:

- Both BMS-986205 and nivolumab should be delayed for
  - Grade  $\geq 2$  toxicity in subjects with baseline AST or ALT within normal limit,
  - Grade  $\geq 3$  toxicity in subjects with baseline AST or ALT within grade 1 toxicity range
  - Drug related increase in AST or ALT at 2x baseline value or when AST or ALT is 8x ULN (whichever is lower) in subjects with baseline AST or ALT in grade 2 toxicity range.
- If AST or ALT levels do not improve with a dose delay of 3 - 5 days or if the levels worsen, initiate steroid therapy at 0.5 - 2 mg/kg/day methylprednisolone or oral equivalent.
- For ALT or AST levels  $> 8x$  ULN, initiate steroid therapy promptly at 1 - 2 mg/kg/day methylprednisolone or oral equivalent
- For all subjects initiating steroids, consult the PI within 24 hours after initiation of steroids. Gastroenterology consult is recommended.
- If AST or ALT levels do not improve within 3- 5 days or the levels worsen after the start of steroid therapy, discuss with the PI the possibility of adding mycophenolate mofetil at 1 g BID.
- Tapering of steroids can start once AST or ALT levels have declined by one CTCAE grade. Taper steroids slowly over no less than 1 month.

As outlined in above, nivolumab and BMS-986205 therapy may resume when AST or ALT have returned to patient's baseline unless the criteria for permanent discontinuation are reached. Subjects who require delay of therapy should be re-evaluated weekly or more frequently if clinically indicated. It is recommended to monitor elevations in AST or ALT approximately every 3-5 days until levels peak or begin to decline. Both therapies can be resumed when re-treatment criteria are met. The PI must be consulted prior to resuming nivolumab for all subjects who required steroid intervention. Tumor assessments for all subjects should continue as per protocol even if study drug dosing is delayed.

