- For participants with baseline up to Grade 2 AST, ALT and/or Total Bilirubin abnormalities, dosing may resume when laboratory values return to baseline and management with corticosteroids, if needed, is complete.
- Any drug-related liver function test (LFT) abnormality that meets the following criteria require discontinuation:
  - AST or ALT >10 x ULN for >2 weeks
  - AST or ALT >15 x ULN irrespective of duration
  - T. Bilirubin >8 x ULN irrespective of duration for subjects with elevated bilirubin at study entry or >5 x ULN for those with normal T bilirubin at entry
- Subjects with AST, ALT, or bilirubin values meeting discontinuation parameters should have treatment permanently discontinued.

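### Section 6.1.4 permanently stops both drugs by default for Grade ≥3 drug-related AST, ALT or bilirubin, Section 5.5.3 delays and allows resumption up to higher limits, and the cross-reference meant to link them is dead

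*Combined protocol and SAP*

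**What the plan says.** Section 6.1.4 lists the events for which both BMS-986205 and nivolumab are permanently discontinued. Laboratory abnormalities at Grade 3 are generally exempt, with listed exceptions. One exception is that, at Grade ≥3, "drug-related AST, ALT or total bilirubin requires discontinuation". The footnote to that line reads "In most cases of Grade 3 AST or ALT elevation, study treatment will be permanently discontinued" and allows continuation if the investigator sees a favourable balance and discusses it with BMS. The footnote does not mention bilirubin. The same list says "Hepatic events should be managed as detailed in Section 5.6.4". It also carries a stop for AST or ALT >3x ULN concurrent with total bilirubin >2x ULN.

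Section 5.5.3 notes that patients may enter with AST or ALT in the Grade 2 range and continues "This requires a protocol-specific approach for the management of hepatic events outlined as follows". Its first action is to delay both drugs. The trigger is Grade ≥2 with a normal baseline, and Grade ≥3 "toxicity in subjects with baseline AST or ALT within grade 1 toxicity range". For a Grade 2 baseline it is the lower of 2x baseline and 8x ULN. It then says "nivolumab and BMS-986205 therapy may resume when AST or ALT have returned to patient's baseline unless the criteria for permanent discontinuation are reached". Its own discontinuation limits are "AST or ALT >10 x ULN for >2 weeks", AST or ALT >15x ULN at any duration, and total bilirubin >5x ULN (normal at entry) or >8x ULN (elevated at entry).

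Section 5.5.1 sends hepatic events to Section 5.5.3.

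**The concern.** The two sections give different default answers to the same question: after a Grade 3 drug-related liver enzyme rise, does the patient come off both drugs for good, or wait and restart? Section 1.3.1 gives observation of liver toxicity in HCC as the reason for starting at 50 mg, so this is a foreseeable decision in this trial.

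The person consulted also differs. Section 6.1.4 requires discussion with BMS before continuing. Section 5.5.3 requires consultation with the PI, and before resuming nivolumab only where steroids were needed.

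At stake are consistent handling of a safety event and time on treatment.

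**Working it through.** The plan states no figure to reproduce here. The check sets the rules side by side and then sizes the overlap.

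**1. The conflict in grades, with no outside cut-point.** Take a patient with Grade 1 baseline AST and a drug-related rise to Grade 3.
- 6.1.4: permanent stop of both drugs by default.
- 5.5.3: Grade ≥3 is the delay trigger, and both drugs may resume at baseline if its stop limits are not reached.

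**2. The cross-reference.** Section 5.6 is the DLT definition. It has no numbered subsections and is followed by 5.7, so there is no 5.6.4. The hepatic section is 5.5.3, as 5.5.1 says. Correcting the number alone would leave the Grade ≥3 stop in the same list as the line deferring to 5.5.3.

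**3. Which section the rest of the protocol follows.** The AST/ALT DLT limits in 5.6 (>10x ULN for more than 2 weeks; >15x ULN) are those of 5.5.3. A phase I patient could be stopped for good under 6.1.4 without meeting a listed hepatic DLT limit.

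**4. Width of the AST/ALT band.** The documents do not give CTCAE cut-points. Let g be the level above which Grade 3 starts, in multiples of ULN. The conflict runs from g to 10x ULN at any duration, and up to 15x ULN for at most 2 weeks.
- Graded against ULN, g = 5 (inferred from the entry limit of 5x ULN and the statement that Grade 2 range patients may enrol): >5x to 10x at any duration, and >10x to 15x for up to 2 weeks.
- Graded against ULN, g = 8 (sensitivity value): >8x to 10x at any duration, and the same upper band.
- Graded against baseline b, with g = 5b (assumption): b = 1.5 gives g = 7.5, so >7.5x to 10x plus the upper band; b = 2 gives g = 10, so the upper band only; b = 3 gives g = 15, so no conflict.

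**5. Example.** Normal baseline, drug-related AST 9x ULN, bilirubin not above 2x ULN so that the concurrent rule is not met. If Grade 3 starts at or below 8x ULN, 6.1.4 stops both drugs by default. Section 5.5.3 holds both, starts steroids promptly because AST is above 8x ULN, and allows resumption at baseline.

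**6. Bilirubin, normal at entry.** If Grade 3 starts above 3x ULN (assumption), the band is >3x to 5x ULN. If it starts at 5x ULN or above, there is none.

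**7. How often a case may arise.** Section 1.4 reports Grade 3/4 AST increase in 4% on nivolumab alone in HCC. Expected cases = 0.04n; chance of at least one = 1 − 0.96^n.
- Full trial, 17 at the MTD plus 3 to 6 at the other dose, n = 20 to 23: 0.80 to 0.92 cases; 1 − 0.96^20 = 0.56 and 1 − 0.96^23 = 0.61.
- Stop at stage 1, 9 plus 3 to 6, n = 12 to 15: 0.48 to 0.60 cases; 1 − 0.96^12 = 0.39 and 1 − 0.96^15 = 0.46.

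These count every Grade 3/4 AST case, not only those in the band, and use the single-agent rate.

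**The case against.** The best defence is that the sections can be read together. Resumption in 5.5.3 is permissive and conditional on no permanent discontinuation criterion being reached. Delay would be the immediate step, 6.1.4 would set the default, and the 5.5.3 limits would be a ceiling for patients continued after discussion with BMS. This does not rescue the text. It makes the resumption rule after a Grade ≥3 delay, and most of the 5.5.3 limits, operative only for patients excepted by BMS. That sits badly with a section written for patients with impaired livers at entry. It also leaves bilirubin with no exception.

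A second defence is that the documents already show 5.5.3 is meant to govern and that 5.6.4 is a numbering slip. That is probably right about intent, and it means precedence is broken rather than absent. The contrary bullet still stands.

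Other parts of the defence hold. The stricter section errs towards stopping. Discussion with BMS (6.1.4), PI consultation (5.5.3) and weekly review (17.2) all soften the effect. The band is widest for normal baselines, while 5.5.3 describes these patients as generally cirrhotic.

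Two stronger readings are tempting but unsupported:
- A reader might infer that the Grade 4 rule in 6.1.4, "Any Grade 4 drug-related AE or laboratory abnormality (including but not limited to creatinine, AST, ALT, or Total Bilirubin"), is a further conflict. It adds nothing if Grade 4 starts above 15x ULN for AST/ALT and 8x ULN for bilirubin, and the documents give no cut-point to show otherwise.
- A reader might see the combined AST/ALT and bilirubin line in 5.5.6 as contradicting the either/or wording in 5.5.3. It most naturally echoes the concurrent >3x and >2x ULN stop in 6.1.4, and it does not say that a single value fails to stop treatment.

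The hepatic algorithm in Appendix 10 has further limits (8x and 5x ULN). It is general guidance, and the line annotates a figure that is not shown, so little rests on it.

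**Conclusion.** The inconsistency is real and should be corrected. For Grade ≥3 drug-related AST, ALT or bilirubin, 6.1.4 and 5.5.3 give opposed defaults, and the sentence that should settle the matter points nowhere.

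The conflict in grades for a Grade 1 baseline needs no assumption about cut-points. The numerical bands do. They narrow as baseline AST/ALT rises if grading is relative to baseline, and at 3x ULN or more they vanish under the 5x-baseline assumption. The frequency figures show only that one relevant decision is plausible in a trial of this size.

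The expected consequence is some unnecessary permanent discontinuation and uneven handling between patients. A reader might infer that the response test is compromised. The documents do not support that: Section 11.5.4 keeps eligible patients who stop early in the response analysis, and alpha, power and sample size do not depend on these rules.

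**What to change.** In the next amendment:
- Correct the 6.1.4 pointer from 5.6.4 to 5.5.3.
- State that 5.5.3 governs hepatic discontinuation. This is the evident intent; the sponsor's clinicians should confirm it.
- Delete the Grade ≥3 AST/ALT/bilirubin bullet and its footnote in 6.1.4, or align them with the 5.5.3 limits.
- Keep the total bilirubin delay trigger in 5.5.1, because the delay bullets in 5.5.3 name only AST and ALT.
- Keep the concurrent AST/ALT >3x and bilirubin >2x ULN stop, and list it in 5.5.3 so that it is not lost when that section takes precedence.
- Leave the combined line in 5.5.6 as it is, or have it cite the concurrent rule by name. Do not change it to an either/or.

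The cost is amendment wording and one clinical decision. No procedures or patients are added.
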